Stage 1. Interview. We will phone screen approximately 120 Gulf War veterans (to obtain the targeted 80 subjects) with symptoms they attribute to service in the 1991 Persian Gulf War who have sought care at UT Southwestern Medical Center (Dr. [name]) or the Dallas VA Medical Center Neurology Clinic (Dr. [name]) for GWI. In addition, we have enrolled two large (>100 subjects enrolled after screening) veterans studies at the Center for BrainHealth using local advertisement and particularly our social networking public relations team. This team includes a combat veteran with extensive experience in using social media outlets to effectively recruit subjects for clinical trials.

The subjects will be screened initially by short telephone interview to determine whether they appear to have a Gulf War Illness, and will be briefly screened for exclusion criteria and the co-existing conditions listed below. The subjects will include men and women, ages 43 to 75 (ages 18 to 50 during the 1991 Gulf War) ofany race/ethnicity, and both enlisted and officer ranks. The potential subjects will then perform over the phone the Controlled Oral Word Association Test (COWAT) for three letters. Performance below 1 sd of the mean is the criterion, in our experience, to warrant further screening with more extensive testing for retrieval deficits (COWAT is a sensitive, brief measure of verbal retrieval). The telephone interview will be conducted

by a trained telephone interviewer. Those meeting the inclusion criteria will then be invited to participate in the second stage of the evaluation and be given an appointment for it.

Stage 2. Screening for a Retrieval Deficit. Those meeting the inclusion criteria will visit the UTD Center for BrainHealth for the study to be fully explained and formal consent obtained by study personnel. Once consent is obtained, the subject will be screened for a retrieval deficit with the neuropsychological tests of the Semantic Object Retrieval Test (SORT), COWAT (both letter and category fluency), Boston Naming Test (BNT), and the California Verbal Learning Test (CVLT). If a subject scores > 2 SD below the mean on any of these tests, the subject will be deemed to have a retrieval deficit and will be enrolled in the treatment phase of the study. These subjects will then be classified under the CDC criteria for GWI subtype and screened for co-morbid conditions/exclusion criteria that could potentially obfuscate the results of a treatment response.

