Stage 3. Pre-Treatment Testing. Those meeting criteria of having an established GWI and retrieval deficit will be scheduled for a neuropsychological test battery and EEG testing (SORT task with EEG, Semantic Selection task with EEG) as outlined under *Neuropsychological Measures and EEG Tasks* below. The two primary outcome measures will be the COWAT and CVLT. Secondary outcome measures will be SORT task behavioral and ERP measures, as well as Semantic Selection task performance and ERP measures.

Expected sample sizes. Our target sample of 80 Gulf War veterans who will complete the treatment phase of the study will afford us power to detect a statistically significant difference. Treatment-related change in verbal fluency and memory measures will be the primary outcome measures. Treatment-related change in verbal fluency and memory measures will be the primary outcome measures. A study of the effects of single-session tDCS applied to PFC on verbal fluency measures in normal controls showed a large effect-size, with standardized mean difference Cohen's d = 1.18.²⁰ Additionally, this treatment effect estimate on healthy controls is comparable to or exceeds the effect-size estimates for verbal fluency deficits in GWVs with GWI: Letter Fluency averaging over S1-3 Cohen's d = 0.69; S2 Cohen's d = 1.12, S3 Cohen's d = 0.85; Category Fluency averaging over S1-3 Cohen's d = 0.61, S2 Cohen's d = 0.81, S3 Cohen's d = .61.¹¹ For the treatment effect-size for S2, Cohen's $d = 1.18^{20}$, a sample size of 40 per group yields Power=0.92, and for the deficit effect-sizes for S2, Cohen's d = 1.12, and for S3 Cohen's d = .61, Power =0.94 and Power =0.89, respectively.

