b. Controlled Oral Word Association Test (COWAT).⁴⁰ This is an assessment of word retrieval during which the patient is required to produce as many words in one minute that begin with either a specific letter (e.g., *F*, *A*, or *S*) or members of a specific category (e.g., *animals*, *fruit and vegetables*). Psychometrics: Cronbach's alpha = .83 for the number of items generated per condition; test-retest reliability r = .74; test-retest also has shown significant gains observed from first (*M*=39.7, *SD*=10.48) to second (*M*=42.5, *SD*=9.9) administration, t(1, 119)=4.19, p<.001.⁴¹

c. Boston Naming Test (BNT).⁴² The test consists of 60 pictures of items where each is presented one at a time for the patient to provide the name of the item depicted. The task will be split into two equivalent 30 item tests (Cronbach alpha = .88; whole sample agreement between forms kappa = .93; Graves et al., 2004). The test assesses visuoperceptual processing, access to semantic knowledge and access to and production of the name of the object, which marked word retrieval from a visual input. Internal consistency ranges from r = .78 to .96 across studies. Test–retest stability in cognitively normal adults varies as a function of time interval and sample composition and ranges from r = .59 to .92.⁴³

d. California Verbal Learning Test (CVLT-II).⁴⁴ The test is a list-learning task where the tester reads aloud a list, called "Monday's shopping list." The list contains sixteen common words, each of which belongs to one of four categories. The tester records how many items the patient remembers over several repeated trials and if the patient is making use of category information. There is also a delayed recall trial after 20 minutes. The test is an indirect measure of word retrieval in that successful word retrieval from semantic memory is needed to perform well in this episodic memory task. The CVLT-II has generally large test-retest correlation coefficients for the primary CVLT-II measures in both the standard/standard (range r = 0.80-0.84) and standard/alternate (range r = 0.61-0.73) cohorts, with reliability coefficients for primary measures ranging from 0.80 (e.g., total trials 1–5) to 0.84 (recognition discriminability).⁴⁵

Parallel versions are available for all of the above neuropsychological tests. Additional neuropsychological measures included will be (organized by domain of cognitive function):

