The efficacy of HD tDCS will be assessed on each outcome. For the cognitive-behavioral measures (i.e., from SORT, COWA, BNT, CVLT, Trails A & B, Color Word Interference, Digits Forward & Backward, Rey-Osterrieth Complex Figures Test, Grooved Pegboard Test, and Beck Depression Inventory), a mixed-model MANOVA initially will be used to test for omnibus group (active vs sham) effects over time (i.e., Group X Time interaction effects). Given a significant multivariate effect, separate univariate mixed-model ANOVAs for each cognitive-behavioral measure will be evaluated for group (active vs sham) effects over time, and significant interaction effects will be followed up by separate pre- versus post-intervention evaluations for each tDCS group. Verbal fluency has been associated with sex, age, and education^{70, 71 but see 72}; thus, these variables will be included in the models. Additionally, potential mediating effects of IQ (based on NAART) and pre-test to post-test change in executive function, simple attention, working memory, processing speed, and depression (measured via Trails A & B, Color Word Interference, Digits Forward & Backward, Rey-Osterrieth Complex Figures Test, Grooved Pegboard Test, and Beck Depression Inventory) will be explored through covariate mediation modeling. For all testing, data will be thresholded for False Discovery Rates (FDR).

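### The Group X Time test uses the pre-treatment COWAT and CVLT scores as a level of Time, not as a covariate; adjusting for them would cut variance by about 13–20% per visit, or 20–29% for the three-visit mean

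*Combined protocol and SAP*

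**What the plan says.** The section on pre-treatment testing (B. Subject Recruitment, Stage 3) states: "The two primary outcome measures will be the COWAT and CVLT". The paragraph on expected sample sizes puts this on a change scale: "Treatment-related change in verbal fluency and memory measures will be the primary outcome measures".

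The first paragraph of the Statistical Plan gives the whole cognitive analysis. A mixed-model MANOVA is used to "test for omnibus group (active vs sham) effects over time (i.e., Group X Time interaction effects". If it is significant, "separate univariate mixed-model ANOVAs for each cognitive-behavioral measure will be evaluated for group (active vs sham) effects over time". The plan then gives the next step for any measure that passes this stage: "significant interaction effects will be followed up by separate pre- versus post-intervention evaluations for each tDCS group". After naming sex, age and education as correlates of verbal fluency, it adds: "thus, these variables will be included in the models". IQ and changes on other tests appear only in exploratory mediation models.

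The plan does not list the levels of Time. It also does not say whether the demographic variables are crossed with Time. Nowhere is the participant's own pre-treatment score on the outcome test named as a covariate.

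**The concern.** Every participant is tested before treatment and at 1 week, 3 months and 6 months after it. If the pre-treatment test is a level of Time, the Group X Time test compares changes from baseline between arms. A change score gives the baseline a weight of exactly one. Covariate adjustment gives it the weight that the data support, which is below one whenever the pre–post correlation is below one and the variances are similar. Under randomisation both approaches estimate the same effect, but the change comparison has the larger variance. It also over-corrects a chance baseline difference between arms, because part of that difference would disappear by regression to the mean.

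The listed covariates do not repair this. A main effect of sex, age or education is constant over visits and cancels from every within-person difference.

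At stake is precision on both primary outcomes in a trial of 80, where the information needed is already collected.

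**Working it through.** **The plan's own figures.** The documents give no precision figure for the Group X Time test. The only power statement (Expected sample sizes) gives 0.92, 0.94 and 0.89 for d = 1.18, 1.12 and .61 with 40 per group. A plain two-sample t test at two-sided .05 has noncentrality d × √(40/2) = 5.28, 5.01 and 2.73, hence power 0.999, 0.999 and 0.77. The stated values are not reproduced. That is a separate matter, and they are not used below.

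**Inputs.**
- COWAT (C. Procedures, 1b): "test-retest reliability r = .74". The retest data there agree. The SD of the difference is (42.5 − 39.7)/4.19 × √120 = 7.32, so r = (10.48² + 9.9² − 7.32²)/(2 × 10.48 × 9.9) = .74.
- CVLT (1d): r = .61–.73 for alternate forms and .80–.84 for the same form. The General Experimental Approach plans alternate forms at follow-up where they exist, so the first range is the relevant one.
- 40 per arm and three follow-ups.
- Assumed: equal variances and one correlation r between any two visits (compound symmetry).

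**Variance per person, in units of the score variance.**
- One follow-up: change 2(1 − r); adjusted 1 − r²; ratio (1 + r)/2.
- Mean of three: change (1 + 2r)/3 + 1 − 2r = 4(1 − r)/3; adjusted (1 + 2r)/3 − r² = (1 − r)(1 + 3r)/3; ratio (1 + 3r)/4.

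| r | One visit: change, adjusted | Saving | Mean of three: change, adjusted | Saving |
|---|---|---|---|---|
| .61 (CVLT alternate, low) | 0.780, 0.628 | 19.5% | 0.520, 0.368 | 29.2% |
| .73 (CVLT alternate, high) | 0.540, 0.467 | 13.5% | 0.360, 0.287 | 20.2% |
| .74 (COWAT) | 0.520, 0.452 | 13.0% | 0.347, 0.279 | 19.5% |
| .80 (CVLT same form, low) | 0.400, 0.360 | 10.0% | 0.267, 0.227 | 15.0% |
| .84 (CVLT same form, high) | 0.320, 0.294 | 8.0% | 0.213, 0.188 | 12.0% |

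The standard error falls by 1 − √ratio. For r = .61–.74 that is 7–10% at one visit and 10–16% for the mean of three. In sample-size terms the three-visit saving equals 1/0.805 to 1/0.708, or about 24–41% more participants.

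**Sensitivity to the assumptions.** With the documents' COWAT SDs (10.48 before, 9.9 after) the savings are 18% and 27%. With r = .61 between baseline and follow-up but .74 or .84 among follow-ups, the three-visit saving is 25% or 23%.

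**Power from baseline handling alone.** This uses the 1-df mean of three follow-ups, two-sided .05 without multiplicity adjustment, and noncentrality d/√(V/20), where V is the per-person variance above.

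| d | r | Change | Adjusted |
|---|---|---|---|
| 0.4 (assumed) | .74 | 0.4/√(0.347/20) = 3.04, power 0.85 | 0.4/√(0.279/20) = 3.39, power 0.92 |
| 0.4 (assumed) | .61 | 2.48, power 0.69 | 2.95, power 0.83 |
| .61 (plan) | .74 | 4.63, power 0.996 | 5.16, power 0.999 |
| .61 (plan) | .61 | 3.78, power 0.962 | 4.50, power 0.993 |

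**Demographics.** In mixed models fitted to simulated data, the standard error of Group X Time was 0.2063 both with and without demographic main effects. Crossed with Time, they lowered it to 0.1713 when age predicted change. When age did not predict change, they did not lower it (0.1528 against 0.1536).

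**The case against.** **The planned test is sound.** Group X Time in a randomised trial is valid and unbiased, and chance imbalance averages out over randomisations. This stands: the point is about efficiency, and a reader should not infer bias.

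**Baseline as a Time level is inferred.** This is true, because the levels are not listed. The pre-versus-post follow-ups and the change-scale wording make the inference strong.

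**A larger loss is tempting.** Participants enter with a phone COWAT more than 1 SD below the mean, and then "the subject will be screened for a retrieval deficit with the neuropsychological tests", with entry at more than 2 SD below on any one of four. Such truncation can lower r, and a reader might infer a loss of up to 45%. For the three-visit mean that needs r = .40, a value the documents do not give. Simulating the cut-offs gave savings of 33–41% for COWAT and 20–43% for CVLT, but with assumed between-test correlations of 0.3 and 0.6. Other set-ups gave 22–48%. A larger saving is plausible but not documented.

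**Demographics could help.** A reader might infer that they cannot sharpen the test at all. That holds only for main effects, and the plan is silent on crossing them with Time.

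**A larger power gain is tempting.** For 0.4 SD the 3-df interaction test has power of about 0.72 (r = .74) or 0.52 (r = .61). Setting these against 0.92 and 0.83 credits baseline adjustment with a gain that comes partly from moving from 3 df to 1 df. That move also assumes a constant effect, whereas Objective #6 allows for further gains by 6 months.

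**At the plan's effects little is lost.** This is correct at d = .61. However, the plan's d = 1.18 comes from a single session in healthy controls, and its d = .61 is the size of a deficit. Neither is a treatment effect in this population, so a smaller effect is worth guarding against.

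**Conclusion.** The point holds as a matter of efficiency. The planned test of COWAT and CVLT is valid but leaves precision unused, because the pre-treatment score is (by strong inference) a level of Time and the named covariates, as main effects, do not sharpen Group X Time.

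Under compound symmetry and the documents' r of .61–.74, adjustment would save about 13–20% of variance at one visit and 20–29% for the mean of three. If the CVLT same-form correlations applied, its saving would be 8–10% and 12–15%. Any larger figure rests on an assumption about how selection lowers r.

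The power figures rest on an assumed constant effect, complete data and unadjusted alpha. They are not the power of the whole procedure, which also passes through the MANOVA and the FDR control. The size is moderate, but the change is worth making because it needs no new data.

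**What to change.** For each cognitive outcome, model the 1-week, 3-month and 6-month scores as the outcomes, with terms for arm, visit, arm-by-visit, the same test's pre-treatment score, sex, age and education. State which pre-treatment score is used if a test is given both at in-person screening and in the pre-treatment battery.

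Name the efficacy test explicitly. Once baseline leaves Time, the arm-by-visit term alone asks only whether the effect differs between visits. The counterpart of the planned test is the joint test of the arm differences at all three follow-ups. Restate the MANOVA step on the same basis and keep the FDR control.

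Making the 1-df average over the three visits the efficacy contrast is a separate, optional choice. It gains power if the effect is steady, and it can dilute an effect that grows by 6 months.

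The cost is a revision of the first paragraph of the Statistical Plan, made before unblinding. No extra visits, tests or participants are needed.

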Objective #4: Each subject will undergo a detailed neuropsychological battery to characterize his or her cognitive and behavioral status—including targeted tests that should be affected by improved verbal retrieval, tests of cognitive functions to which the treatment may generalize, and tests consisting of purportedly unrelated functions to account for global, generalized cognitive improvement. They will also undergo pre-treatment EEG (SORT task with EEG, Semantic Selection task with EEG). These will be used as outcome measures for the treatment trial. The two primary outcome measures will be the COWAT and CVLT. Secondary outcome measures will be SORT and Semantic Selection task, performance and ERP for both sets of tasks.

Objective #5: These subjects will then be enrolled in the active treatment aspect of the study. Enrollment of 80 participants is the target for enrollment in the active phase of the treatment trial. Half the subjects will first receive HD tDCS at 1 mA for 20 minutes over the preSMA region for 10 daily sessions (1 session 5 days per week for a 2 week period). The remaining subjects will initially receive sham HD tDCS; after all follow-up evaluations are completed, they will receive the active HD tDCS treatment.

Objective #6: Each subject will receive follow-up neuropsychological and EEG testing at 1 week, 3 months, and 6 months after treatment. This last time point for evaluation extends from our preliminary work showing that later, further improvement in electromodulation treatments can occur at 6 months post-treatment. HD tDCS active treatment subjects enrolled early in the study will be followed longer than 6 months if agreeable to assess length of effect.

Following completion of this clinical trial, we will be able to determine whether HD tDCS is an effective treatment for the verbal retrieval deficits associated with GWI. An HD tDCS cap is a relatively inexpensive piece of equipment that can be re-used many times for multiple patient treatments. These caps are readily available, and the application of the treatment regimen is straightforward to administer. Thus, this treatment can be utilized in any VA medical center or clinic around the nation. In addition, the neuro-psychological tests and ERP/time frequency findings may function as clinical markers for diagnosis and treatment efficacy in subsequent treatment trials to measure treatment response.

SPECIFIC AIMS

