Hypothesis #2c: An increase in false negative errors and a decreased "Go"P3 ERP response on the Semantic Selection Tasks is indicative of an impaired ability to select a correct memory for retrieval.³³ Conversely, there will be increased false positive errors and a decreased "NoGo" P3 ERP on the Semantic Selection Tasks if a patient cannot inhibit an incorrect memory. *We hypothesize that following HD tDCS therapy, there will be a normalization of the patient's behavior (reduced errors, improved RTs) and/or ERP responses (increased P3 amplitudes for Go and/or NoGo trials) due to modulation of the retrieval circuit, with the changes based on the pre-treatment impaired retrieval function (selection and/or inhibition).*

CLINICAL TRIAL

A. General Experimental Approach.

1. We will screen 120 GWI patients who report subjective word-retrieval deficits over the phone with the COWAT.

2. A subject who on the phone screen has a subjective complaint and decrement in COWAT performance will then be consented and enrolled in person at CBH, and then screened to determine that they have GWI and objective evidence of a verbal retrieval impairment on neuropsychological testing.

3. If a subject scores > 2 SD below the mean on any of the following – the SORT clinical test, COWAT, BNT, and/or CAVLT, the subject will be enrolled in the treatment phase of the study and classified using the CDC criteria for subtype of Gulf War Illness.

4. Subjects will undergo a pre-treatment battery of detailed neuropsychological tests and EEG (SORT and Semantic Selection tasks with ERP). These will be used as outcome measures for the treatment trial.

5. We will enroll 80 subjects in treatment with one-half of the subjects receiving HD tDCS at 1 mA for 20 minutes over the preSMA region for 10 daily sessions; the other half of the subjects will initially receive sham HD tDCS and, after all follow-up evaluations are completed, they will receive active HD tDCS treatment. Participants will be randomly assigned to stimulation and sham conditions via algorithm.

6. Determine at 1 week, 3 months, and 6 months post-last-treatment whether the therapy has been effective by repeating the outcome measures (parallel versions when available) of the SORT, COWAT, BNT, CVLT, and ERP tasks.

B. Subject Recruitment

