After removing artifacts and segmenting EEG data into multiple trial-by-trial EEG epochs (-200 ms to 1800 ms for SORT and to 1500 ms for SIT), we will apply the STAT-PCA technique that we published, and with which we have longitudinal experience ^{32, 73} for ERP and time frequency data. Baseline corrected ERPs at each space-time (ST) point, and log normalized squared absolute values at each space, time, frequency (STF) point will be calculated and used as input for the inferential stage of STAT-PCA. The statistical model will include the additive effects of group (active vs sham) and time and higher-order additive effects of group, time, and condition (SORT: Bind vs Nonbind; Semantic Selection: Trial-Type [Go vs No-Go] X Categorization [Simple vs. Moderate vs. Complex) on ERP at each space-time point and log power at each STF. Both withinand between-subject variance components will be included. Interaction contrast *t*-statistics for each ERP ST and spectral STF point will be calculated to assess the influence of the interaction terms on log power, and planned t-contrasts will be calculated from condition differences between the groups. Mean differences that survive a threshold of 5% FDR will be stored as a ST and STF arrays and entered into the sequential PCA. For ERP data, the ST array will be put in a matrix in which columns index space and rows index time. For ERP data, PCA will be performed and will return a set of eigenvalues and eigenvectors, which will be subjected to Parallel Analysis ⁷⁴ to determine the number of factors to retain. Only eigenvalues above the 95% confidence intervals of the null distribution will be retained. The retained eigenvectors will be varimax rotated and used to calculate the factor scores by projecting the original dataset onto the eigenvectors. The resulting factor scores will be reshaped such that the columns index electrodes and the rows index time points, and PCA will be performed on this matrix. Factor retention will be determined as in the first sequence. The resulting eigenvectors will represent topographies and their corresponding factor scores will represent the time courses for the interaction effects.

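### For the cognitive outcomes, including both primaries, a significant Group x Time interaction is followed up only within each arm; Time and post are undefined, and no active-versus-sham estimate or confidence interval is specified at any visit

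*Combined protocol and SAP*

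**What the plan says.** Section B, Stage 3 names the primaries: "The two primary outcome measures will be the COWAT and CVLT". The first paragraph of the Statistical Plan tests all cognitive measures with a mixed-model MANOVA for Group x Time. If that is significant, a univariate mixed-model ANOVA follows for each measure. The only step after a significant univariate interaction is that "significant interaction effects will be followed up by separate pre- versus post-intervention evaluations for each tDCS group". The paragraph does not list the levels of Time and does not tie post to a visit. It applies false discovery rate control to all testing, but gives no level or family for the cognitive measures.

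The question is put by visit. Clinical Trial section A, item 6, reads: "Determine at 1 week, 3 months, and 6 months post-last-treatment whether the therapy has been effective". Objective #6 justifies the last visit by earlier work in which "later, further improvement in electromodulation treatments can occur at 6 months post-treatment".

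For the EEG data, the second paragraph of the Statistical Plan does provide between-arm contrasts: "planned t-contrasts will be calculated from condition differences between the groups". It names no visit for them. No between-arm contrast, estimated difference or confidence interval at a visit is given for the cognitive measures.

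**The concern.** When benefit appears and how long it lasts are stated questions of this trial. With baseline and three follow-up visits, a significant interaction says that the two arms' profiles differ somewhere. It does not say at which visit, or by how much. The planned follow-up then turns to each arm alone. If post pools the visits, the follow-up carries no information about visits. If it is read visit by visit, any gain that both arms share, such as practice, stays in each within-arm change. A significant change in one arm and a non-significant change in the other is not a test of the difference between them.

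Two misreadings could follow. A benefit that has faded could look as if it persists, because one arm happens to cross 0.05 and the other does not. A lasting benefit could be obscured because both arms improve significantly. Subtracting the two mean changes still gives the point difference at a visit. Its test and its interval are what the plan lacks.

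**Working it through.** **Inputs.** COWAT figures are from section C.1.b: first administration mean 39.7 (SD 10.48), second 42.5 (SD 9.9), r = .74, t = 4.19 with 119 df. Allocation is 40 per arm (section A, item 5). Assumptions: four Time levels, equal correlation between visits, two-sided 0.05, no dropout, and a true effect of 0.5 SD = 0.5 × 10.48 = 5.24 words. Rates are given a significant univariate interaction, F(3, 234). The MANOVA gate is not modelled.

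**Step 1: reproduce the plan's retest figure.** SD of change = √(10.48² + 9.9² − 2 × .74 × 10.48 × 9.9) = √(109.83 + 98.01 − 153.55) = 7.37 words. The gain is 42.5 − 39.7 = 2.8 words. At n = 120, t = 2.8 / (7.37/√120) = 4.16, against the stated 4.19. The inputs are consistent.

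**Step 2: one arm, no treatment effect at that visit.** The standard error of mean change in 40 people is 7.37/√40 = 1.165. A shared gain of 2.8 words gives an expected t of 2.8/1.165 = 2.40, and the pre/post test is significant with probability p = .65 (noncentral t, 39 df). With both arms in this position, active significant and sham not has probability p(1 − p) = .65 × .35 = .23. For gains of 1.4, 0.7 and 0 words, p is .216, .090 and .05, and p(1 − p) is .17, .08 and .05.

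**Step 3: simulation with the interaction gate.** The effect is at 1 week only and the result is read at 6 months. The gate is passed in about 92–93% of trials. Among those:

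| Shared gain (words) | Active significant, sham not | Sham significant, active not | Baseline-adjusted active-versus-sham test significant |
|---|---|---|---|
| 2.8 | 23% | 23% | 5% |
| 1.4 | 17% | 17% | 5% |
| 0.7 | 8.5% | 8% | 5% |
| 0 | 5% | 5% | 5% |

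The pattern does not need an early transient effect. With benefit at 6 months only, the 1-week rates for active significant and sham not are 23%, 17.5%, 8.6% and 5%.

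**Step 4: a lasting 0.5 SD effect.** Both arms are significant (two-sided) at 6 months in about 62%, 18%, 7% and 4% of gated trials at gains of 2.8, 1.4, 0.7 and 0 words.

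**Step 5: the interval that is not specified.** The baseline-adjusted residual SD is 9.9 × √(1 − .74²) = 6.66 words. The 95% half-width is 1.99 × 6.66 × √(2/40) = 2.96, or about ±3.0 words (0.28 baseline SD). The simulation gives 2.97 to 2.98. Without baseline adjustment it is 1.99 × 7.37 × √(2/40), about ±3.3 words.

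**CVLT.** The documents give no retest gain. For reliability with alternate forms they give "standard/alternate (range r = 0.61-0.73) cohorts". If the gain is assumed to lie between 0 and 0.27 SD (2.8/10.48, borrowed from COWAT), the Step 3 rate for active significant and sham not runs from 5% to 26%.

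**The case against.** The strongest reply is that the interaction already compares active with sham. That stands: it is a valid randomised test, and the within-arm step is reached only after it. A reader might infer from the rates above that the plan has an inflated error rate, or that it has no active-versus-sham test at all. The documents support neither inference.

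Second, the plan never says that Time has four levels. If Time were pre/post and the model were run once per visit, the interaction would itself be the between-arm test at that visit. This reading cannot be excluded, but the plan does not state it. One repeated-measures factor fits the three-visit schedule better. Even on the pre/post reading, no estimate or interval is specified.

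Third, the 23% needs a 2.8-word shared gain, and that figure may not apply. The cited source reports that "test-retest also has shown significant gains observed from first" to second administration. Here COWAT has already been used by phone ("The potential subjects will then perform over the phone the Controlled Oral Word Association Test (COWAT) for three letters") and again at the in-person screen, and parallel forms are planned where available. The shared gain after baseline is unknown and may be smaller. The excess over 5% is small at 0.7 words and absent at zero. With false discovery rate control over the six within-arm COWAT tests (Benjamini-Hochberg; this family is an assumption), the four rates are 21%, 11%, 4% and 2%.

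Fourth, the plan does not say that active significant and sham not will be read as a difference between arms. The reverse pattern is equally common, so a bias towards active stimulation cannot be claimed. Likewise, both arms being significant under a lasting effect is not a false conclusion. It just does not show the size of the arm difference.

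Last, the comparison with the EEG paragraph is limited, because those contrasts name no visit either.

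**Conclusion.** The point holds as a gap in the analysis of the cognitive outcomes, including both primaries, and should be fixed. The plan asks about effectiveness at three visits, defines neither Time nor post, and offers only within-arm follow-up. It specifies no active-versus-sham estimate or interval at any visit. That gap does not depend on the size of any practice gain.

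The rates illustrate a risk of misreading. For a benefit confined to 1 week, the chance of active significant and sham not at 6 months runs from about 23% (2.8-word gain) down to 5% (no gain), against 5% for the direct comparison. These rates rest on the cited COWAT SDs and correlation, 40 completers per arm, four Time levels, equal correlations, a 0.5 SD effect and an unmodelled MANOVA gate. They are not error rates of the plan. The omnibus randomised comparison is unaffected.

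**What to change.** Replace the follow-up sentence in the first paragraph of the Statistical Plan with:

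> Time has four levels (baseline, 1 week, 3 months, 6 months). For COWAT and CVLT, active-minus-sham differences at 1 week, 3 months and 6 months, adjusted for baseline score, age, sex and education, will be estimated with 95% CIs from one repeated-measures model and reported whether or not the omnibus tests are significant. Significance claims for these six contrasts follow the omnibus gate and FDR control at 5% within this family. The other cognitive measures get the same estimates as supportive results. Within-arm changes are descriptive only.

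The level and family are written out because the plan states 5% only for the EEG data. Hypothesis #2a should not be presented as tested by these differences. It asks whether treated patients reach expected premorbid levels, and active could beat sham while both stay below that level. It remains a separate, descriptive question.

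The cost is a rewording, a little more analysis and no new data. Six contrasts under FDR take some power. For a lasting 0.5 SD effect on COWAT, the chance of passing the univariate gate and the 6-month contrast is about .88 at 0.05 and .76 at the strictest step (.05/6 = .0083). For CVLT at r = .61 to .73 it is .64 to .83 and .49 to .68. All are somewhat lower once the MANOVA gate, which the plan already imposes, is counted.
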